10.2 SAMPLE SIZE DETERMINATION

Power and Sample Size Determination

The trial uses a fixed sample design. We assumed a prevalence of cognitive impairment of 0.40 for this at population, a sample size of N=1074, we require a minimum risk difference of 0.09 ($q = p_1 - p_0 < -0.09$) to attain statistical power of at least 80 percent. We assumed a prevalence of cognitive impairment of 0.40, however, the risk difference of 0.09 attains the targeted level of power or higher, for a prevalence in a reasonable range (e.g., 0.2-0.8). To achieve power of at least 80 percent for the targeted sample size of N=1,074, we require a difference in the means to be greater than 0.17 standard deviations on a standardized scale. For the SF-36 mental component summary (MCS), for example, if the SD is conservatively equal to 30, then the minimum difference in the mean MCS scores will need to be approximately 5.1 points (i.e., min difference = $0.17 * SD = 0.17 * 30$). For the physical component summary (PCS), if the population SD were 40 points, the minimum difference would be 6.8 points (min difference = $0.17 * 40$). These power and effect size calculations assume an independent, two-sample test, an alpha level of five percent and all statistical tests are two-sided tests.

The target sample size for the study is 1,074 patients (537 per treatment arm), in order to achieve power of 80% for each test of the primary outcomes. The study is powered for meaningful minimum effect sizes to detect treatment differences in the primary endpoints. The statistical software STATA vers. 15 (Stata Corporation, College Station, TX) and R have been used to compute the statistical power.

Based on 2016 data, emergency intubations occurred primarily in the Emergency Department (ED) and in the hospital: approximately 200 intubations were performed in the ED and 404 intubations occurred in the hospital, yielding approximately 600 emergency intubations per year. With a projected enrollment period of 36 months, we anticipate adequate feasibility to accrue the required sample size.

Missing Data

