10.4.2 ANALYSIS OF THE PRIMARY EFFICACY ENDPOINT(S)

Analysis of Safety Primary Endpoint

One objective of this study is to establish that the experimental treatment, EVAC-PU-ETT, has a safety profile that is not inferior to the standard treatment, PVC-ETT. For this aim, we will conduct a non-inferiority analysis and test that the underlying population risk of laryngeal injury for the EVAC-PU-ETT treatment group is not statistically higher than the population risk of laryngeal injury for the PVC-ETT treatment group. To evaluate the non-inferiority of laryngeal risk of the EVAC-PU-ETT treatment, we specify a non-inferiority bound that the difference in the true risk probabilities is less than or equal to 0.05. That is, $q = p_1 - p_0 < 0.05$, where p_1 denotes the risk of laryngeal injury for the EVAC-PU-ETT treatment group, p_0 denotes the risk of laryngeal injury for the PVC-ETT treatment group and therefore,

q , denotes the difference in the two risk probabilities. The test of hypothesis for the primary endpoint is a two-sample difference in risk in a group sequential design with one planned interim analysis. The analysis will be conducted when approximately 50 percent of the total sample has been collected. The group sequential stopping rule is based on 2.5 percent significance level and a one-sided stopping rule with an O'Brien-Fleming boundary. The interim analysis would take place when approximately 537 (269 patients per study arm) have been accrued. At the time of the interim analysis, the trial would be stopped if the estimated risk difference, $p_1 - p_0$, is greater than the safety boundary of 0.0956, indicating EVAC-PU-ETT is significantly more harmful than PVC-ETT. Evaluation of the estimated differences will be obtained using standard, fixed-sample maximum likelihood estimates (MLEs). The MLEs provide valid point estimates for evaluating the group sequential design stopping rules. At the conclusion of the study, the estimated difference, confidence intervals and associated p-values require adjustment, accounting for the interim analyses. We consider bias adjusted estimates ⁴ and Rao-Blackwell adjusted estimates ⁵ to correct for the bias in the fixed sample MLEs. Sample mean ordering ⁵ will be used to adjust confidence intervals and p-values.

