Specifically, we will evaluate whether there is a difference in the laryngeal injury risk probabilities for the two treatments, we will use maximum likelihood estimation (binomial family) with an identity link function. The statistical model used for this analysis will be: $p(X) = \beta_0 + \beta_1 X$ where $p(X)$ denotes the laryngeal injury probability and X is an indicator denoting the treatment assignment (1 = EVAC-PU-ETT, 0 = PVC-ETT). The identity link function makes the interpretation of parameter for the treatment effect, β_1 , be equal to $\beta_1 = p(1) - p(0)$, which is exactly the risk difference, q , noted above. In the Prevent pilot study, the estimated risk of laryngeal injury was 0.39 for the PVC-ETT treatment group and 0.38 for the EVAC-PU-ETT treatment group. Assuming an estimated risk difference less than or equal to 0.05 for the targeted sample size of $N=1074$ (537 patients per treatment arm) for the pre-specified alpha-level and statistical design, the statistical power for concluding non-inferiority of the EVAC-PU-ETT treatment group would be 80 percent.

Analysis of Quality of Life Primary Endpoint

We will evaluate whether there are differences in quality of life measures between treatment groups by comparing mean scores. Separate analyses will be conducted for the two endpoints. The statistical model will be linear regression, $\mu(X) = \beta_0 + \beta_1 X$, where $\mu(X)$ denotes the mean SF-36 score, X is an indicator denoting the treatment assignment as before. The test for a treatment effect is denoted by, $\beta_1 = \mu(1) - \mu(0)$. We will use robust inference so that our tests will be valid for modest departures in modeling assumption. Additionally, we will transform the scores to reflect “percent of healthy life”. This transformation of the SF-36 measures provides easily interpretable variables and allow for the retention of patients that die during the study. As noted previously, the design for this endpoint is a fixed sample design. To have power of at least 80 percent for the targeted sample size of $N=1074$, we require a difference in the means to be greater than 0.17 standard deviations on a standardized scale. These

power and effect size calculations assume an independent, two-sample test, an alpha level of five percent and all statistical tests are two-sided tests.

Analysis of Cognitive Impairment Primary Endpoint

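### The 80% power stated for the non-inferiority safety endpoint is wrong: on the plan's own inputs it is about 39% if the tubes are equally safe and 52% at the pilot difference.

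*Combined protocol and SAP*

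**What the plan says.** Section 10.4.2, under the safety primary endpoint, defines the test on the difference in laryngeal injury risk, EVAC-PU-ETT minus PVC-ETT: "we specify a non-inferiority bound that the difference in the true risk probabilities is less than or equal to 0.05". The group sequential stopping rule is "based on 2.5 percent significance level and a one-sided stopping rule", with an O'Brien-Fleming boundary and one interim look at about half the sample. From the pilot study, "the estimated risk of laryngeal injury was 0.39 for the PVC-ETT treatment group and 0.38 for the EVAC-PU-ETT treatment group". The power statement comes next. It opens with the condition "Assuming an estimated risk difference less than or equal to 0.05", takes 1,074 patients (537 per arm), and concludes that "the statistical power for concluding non-inferiority of the EVAC-PU-ETT treatment group would be 80 percent".

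Section 10.2 says the sample size was chosen "in order to achieve power of 80% for each test of the primary outcomes". Section 10.1 lists safety among the primary clinical endpoints and says it will be tested for non-inferiority.

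**The concern.** A non-inferiority test can be well powered only if the margin is wide relative to the standard error. With a risk near 0.39 and 537 per arm, a margin of 5 percentage points is narrow. The condition on the power statement also looks wrong. Power is calculated at an assumed true difference, not an estimated one, and the only value named is the margin itself.

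The central hypothesis that the modified tube is as safe as the standard one rests on this test. If the tubes are in fact equally safe, the trial is more likely than not to miss non-inferiority, and that result would be misread as coming from a well-powered comparison. The trial enrols under exception from informed consent, so an IRB, DSMB or funder relying on 80% would be misinformed about how likely the trial is to answer its safety question.

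**Working it through.** **Inputs, all from section 10.4.2.** Margin 0.05; one-sided level 0.025 (z = 1.96); 537 per arm; p0 = 0.39 (PVC-ETT); p1 = 0.38 (EVAC-PU-ETT) in the pilot. No single true difference is given for the power calculation, so two are used: zero (p1 = p0 = 0.39) and the pilot difference (-0.01).

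**Formula.** Power = Φ[(0.05 - (p1 - p0))/SE - 1.96], with SE = √[p0(1 - p0)/n + p1(1 - p1)/n].

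**Attempt to reproduce the 80%.**

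- Equal risks: SE = √(2 × 0.39 × 0.61/537) = 0.02977. 0.05/0.02977 = 1.680. Power = Φ(1.680 - 1.960) = Φ(-0.280) = **39.0%**.
- Pilot risks: SE = √[(0.39 × 0.61 + 0.38 × 0.62)/537] = 0.02969. 0.06/0.02969 = 2.021. Power = Φ(2.021 - 1.960) = Φ(0.061) = **52.4%**.

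Put another way, the test succeeds only if the observed difference is below about 0.05 - 1.96 × 0.02977 = -0.008. The new tube must look better than the standard one.

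A 400,000-run binomial simulation of the two-stage design, with the 0.0956 harm stop and the 1.96 critical value, gave 39.0% and 52.3%. The interim rule is therefore not the explanation.

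**Other readings at 537 per arm.**

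| Variant | No difference | Pilot difference |
|---|---|---|
| As stated, one-sided 2.5% | 39.0% | 52.4% |
| O'Brien-Fleming final value 1.977 | 38.3% | 51.7% |
| Continuity correction | 36.6% | 49.9% |
| One-sided 5% | 51.4% | 64.6% |
| One-sided 10% | 65.5% | 77.0% |

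None reaches 80%. The statement also fails if it is read as two-sided power to detect a harm of 0.05 (0.39 versus 0.44): that is 38%.

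**The stated condition.** If the true difference equals the margin, the power is Φ(0 - 1.96) = 2.5%, which is the type I error rate by construction.

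**What 80% would require**, with (1.96 + 0.8416)² = 7.849:

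- Sample size, no difference: 7.849 × 2 × 0.2379/0.05² = 1,494 per arm.
- Sample size, pilot difference: 7.849 × (0.2379 + 0.2356)/0.06² = 1,033 per arm.
- At 537 per arm and no difference, a margin of 2.8016 × 0.02977 = 0.083.
- At 537 per arm and margin 0.05, a true difference of about -0.033, or a common risk of about 0.094.

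**Missing outcomes.** The plan gives no attrition rate. If 80% or 60% were assessed at 6 months (my assumption, to show the range), power would be 32% or 26% at no difference, and 44% or 35% at the pilot difference.

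**The case against.** The best counter-argument is that some inputs are inferred.

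- **Baseline risk.** The plan reports the pilot risks but does not say outright that they are the power assumption. The interim boundary of 0.0956 also does not fit a risk of 0.39. With 269 per arm, a zero-centred O'Brien-Fleming bound would be about 2.797 × √(2 × 0.39 × 0.61/269) = 0.118, whereas 0.0956 fits a risk near 0.195. The design may have been computed with other inputs. That is fair, but at 0.195 power is still only about 54% with no difference and 71% with a one-point benefit.
- **Level.** The 2.5% is attached to the stopping rule rather than to the final non-inferiority conclusion. As the table shows, more lenient levels do not rescue the figure.
- **True difference.** The 39% needs equal true risks, which is a usual non-inferiority assumption but not one the plan states. At the pilot values the trial is slightly more likely to succeed than fail. Both figures should be shown.
- **Status of the endpoint.** Section 10.2 calculates power only for cognition and the SF-36, and section 4 lists safety under secondary endpoints. But sections 10.1 and 10.4.2 call safety primary, so the 80% claim in 10.2 covers it. The error does not affect the power calculations for the other endpoints.

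One near match exists. If 1,074 is entered as the per-arm number, power at the pilot difference is 81.5%. That may explain the figure, but it is a guess and contradicts the stated 537 per arm.

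**Conclusion.** The stated 80% is wrong. With margin 0.05, one-sided 2.5% and 537 per arm, power is about 39% if both risks are 0.39 and about 52% if they are 0.39 and 0.38. This assumes that the pilot risks apply, that the 2.5% level governs the final test, and that all 1,074 patients have an outcome. The last assumption is favourable, so actual power would be lower. No variant tried at 537 per arm with the plan's margin and pilot risks reaches 80%. The condition on the estimated difference is invalid in its own right.

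**What to change.** In section 10.4.2, replace the power sentence with, for example: With 537 per arm, control risk 0.39, margin 0.05 and one-sided alpha 0.025, power to conclude non-inferiority is about 39% if the true risks are equal and about 52% if they are 0.38 (EVAC-PU-ETT) and 0.39 (PVC-ETT). If other inputs were used, the authors should state the risk, true difference and alpha, and recompute. In addition:

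- Remove the condition on the estimated difference and name the true difference assumed.
- Give the power at the number expected to be assessed at 6 months.
- State that non-inferiority is concluded only if the upper limit of the adjusted two-sided 95% confidence interval for p1 - p0 lies below 0.05.
- In section 10.2, say that the claim of 80% power for each primary test does not extend to safety.

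The change costs wording in two sections, with no extra patients or procedures. The price is a less favourable figure, which may lead the oversight bodies to ask about the margin or the sample size.

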2 PROTOCOL SUMMARY

2.1 SYNOPSIS

Title: Randomized Trial of Endotracheal Tubes to Prevent Ventilator-Associated Pneumonia – Prevent 2 Study

Study Description: The study will be a Phase II randomized, controlled trial that will equally randomize 1,074 patients requiring emergency endotracheal intubation to receive either a polyurethane-cuffed endotracheal tube equipped with continuous aspiration of subglottic secretions designed to prevent ventilator-associated pneumonia (EVAC-PU-ETT) or a conventional, polyvinylchloride-cuffed endotracheal tube (PVC-ETT). Using a pragmatic approach, we will determine if, by reducing the incidence of ventilator-associated pneumonia, the modified endotracheal tube (ETT) improves long-term quality of life and cognitive function, and if it is as safe as the conventional endotracheal tube, thus providing much needed evidence supporting decision-making.

Objectives: The primary objectives of the proposed trial are to compare the safety and effectiveness of EVAC-PU-ETT and PVC-ETT, initiated at the time of first emergency intubation in the ER or in-hospital. The specific aims are

as follows:

Primary Specific Aim: We will determine if long-term patient quality of life and cognitive function are better using EVAC-PU-ETT compared with PVC-ETT.

For the primary effectiveness endpoint, we will determine if the effect of EVAC-PU-ETT on quality of life (physical and mental component summary), as measured by the 36-item Short-Form General Health Survey, is better compared with PVC-ETT, at 6 months after randomization. An additional patient-centered endpoint will be the proportion of patients cognitively impaired, assessed by the National Alzheimer Coordinating Center's Uniform Data Set.

Secondary Specific Aims: We will determine if EVAC-PU-ETT is as safe as PVC-ETT. We will also determine if EVAC-PU-ETT reduces Infection Related Ventilator-Associated Complications (IVACs) and is more cost effective than PVC-ETT.

Aim 2. For our safety endpoint, we will evaluate the safety profile of EVAC-PU-ETT based on airway-related complications, compared with the PVC-ETT, at 6 months after randomization.

Aim 3. To determine if the EVAC-PU-ETT is effective in reducing the incidence of Center for Disease Control (CDC)-defined IVACs and Ventilator-Associated Events (VAEs) compared with PVC-ETT.

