10 STATISTICAL CONSIDERATIONS

10.1 STATISTICAL HYPOTHESES

Our central hypothesis is that EVAC-PU-ETT is as safe as the standard PVC-ETT and is superior to the standard PVC-ETT in reducing the occurrence of VAP and several of its long-term consequences.

The primary objectives of the proposed trial are to compare the clinical safety and effectiveness of EVAC-PU-ETT compared with PVC-ETT. The primary clinical endpoints will be: safety, quality of life, and cognitive impairment. Safety, measured as long-term laryngeal injury, will be tested for equivalence between the two treatment groups, or more precisely, that the EVAC-PU-ETT treatment is “non-inferior” to the PVC-ETT treatment. Quality of life will be assessed using the RAND Short Form Health Survey (SF-36) Physical Component Summary (PCS) and Mental Component Summary (MCS). For cognitive impairment, patients will be considered cognitively impaired if their global cognition scores are at least 1.5 standard deviation (SD) below the population mean (for comparable patients with moderate TBI) in at least two global cognition scores or more than 2 SD below the population mean for a single global cognition score. Safety will be analyzed using a sequential design with one interim analysis. The primary aims for quality of life and cognitive impairment will be evaluated for superiority of the EVAC-PU-ETT treatment using a fixed sample design. The treatment effect will be measured as the difference in probability risks, between the treatment groups, for the safety and cognitive impairment outcomes. The

treatment effect for the quantitative quality of life outcomes will be represented as differences in means.

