10.4.3 ANALYSIS OF THE SECONDARY ENDPOINT(S)

Analyses of Secondary Endpoints

Important secondary analyses will be conducted to compare means between the EVAC-PU-ETT and PVC-ETT treatments for quantitative outcomes (e.g., domain scores for the SF-36, cost, length of stay) using linear regression. For binary outcomes we will use logistic regression with robust (sandwich) standard error corrections. Comparison of survival outcomes between the EVAC-PU-ETT and PVC-ETT treatments (e.g., time to extubation, time to discharge from the ICU) will be performed using log rank test statistics. We will compare 6-month mortality between the two treatment groups using 6-month mortality estimates from the treatment groups' Kaplan-Meier curves. We will compare mean hospital length of stay, mean ventilator-free days and the mean SOFA scores between EVAC-PU-ETT and PVC-ETT using censored regression analysis. We will investigate whether the proportion of IVAC and VAEs differs between EVAC-PU-ETT and PVC-ETT among the subgroups of critically ill patients defined by gender and race. Formal comparisons between the treatment groups and patient subgroups will be investigated by fitting logistic regression models with robust variance estimates. We will perform omnibus tests of appropriately specified interaction terms between treatment assignment and patient subgroups. The mean and median overall per patient costs will be assessed for each randomized group, along with the clinical and hospital outcomes (consequences). We will investigate the mean difference in cost between the use of EVAC-PU-ETT and PVC-ETT. Cost will be defined in two ways: service-price and billable costs. We will formally test the difference in mean cost by using linear regression analysis with robust variance estimates. Inference on mean cost will be valid provided the sample size is moderately large (e.g.,

greater than 200 patients).⁷ We will use regression analysis to determine if there are greater/lesser benefits/risks in patient subgroups in the economic analysis. We will test for differences in median costs using randomization tests. All hypothesis tests described above will be two-sided. Test results will be deemed statistically significant if the associated p-values of the tests are less than 5 percent.

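### PCS, MCS and cognitive impairment are each tested as primary at unadjusted two-sided 5%, with no success rule or multiplicity control, and the documents rank safety and cognition inconsistently

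*Combined protocol and SAP*

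**What the plan says.** Section 10.1 lists the primaries: "The primary clinical endpoints will be: safety, quality of life, and cognitive impairment". It assesses quality of life through PCS and MCS, and tests quality of life and cognition for superiority in a fixed-sample design. Section 10.4.2 says of PCS and MCS: "Separate analyses will be conducted for the two endpoints". It then gives cognitive impairment its own primary analysis.

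Section 10.2 sets 537 patients per arm "in order to achieve power of 80% for each test of the primary outcomes", at "an alpha level of five percent and all statistical tests are two-sided tests". Section 10.4.2 repeats that level for quality of life. Section 10.4.3, on secondary endpoints, ends: "Test results will be deemed statistically significant if the associated p-values of the tests are less than 5 percent". No section gives an order, an alpha split, a gatekeeper or a definition of success for the primaries.

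The ranking of endpoints varies:

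- **Safety** is part of the primary aim in Section 4 and is primary in Sections 10.1 and 10.4.2. The synopsis puts it elsewhere: "Secondary Specific Aims: We will determine if EVAC-PU-ETT is as safe as PVC-ETT". Section 4 repeats it among the secondary aims and lists it as a secondary endpoint. The primary-endpoint paragraphs of the synopsis and Section 4 name only quality of life and cognition as primary.
- **Cognition** appears in the objectives of the synopsis and Section 4 as follows: "An additional patient-centered endpoint will be the proportion of patients cognitively impaired". The endpoint paragraphs of the same two sections, and Sections 10.1 and 10.4.2, make it primary.

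**The concern.** Three primary tests at 5% each do not add up to one 5% trial unless a rule says how they combine. Without that rule, the stated alpha and power describe single tests and not the primary aim. A sponsor with one significant result out of three could report the aim as met, and a critic could report it as missed; the plan would settle neither. Section 11.1.2 also lists the primary endpoint having been met as a ground for stopping, which cannot be applied while success is undefined. The shifting labels leave open which tests belong to the primary family.

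**Working it through.** **Inputs from the documents.** 537 per arm; two-sided alpha 0.05; 0.17 SD for PCS and MCS; risk difference 0.09 at prevalence 0.40 for cognition, read as 0.40 vs 0.31. **Assumptions.** The documents give no correlations between endpoints, so a common correlation of 0 to 0.6 between test statistics is used. All 537 per arm are taken as evaluable.

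**1. The plan's own power.**
- PCS or MCS: expected z = 0.17 × √(537/2) = 2.786. Power = Φ(2.786 − 1.960) = 79.5%. The difference detectable with 80% power is (1.960 + 0.842) × √(2/537) = 0.171 SD.
- Cognition: pooled SE = √(2 × 0.355 × 0.645/537) = 0.0292; unpooled SE = √((0.40 × 0.60 + 0.31 × 0.69)/537) = 0.0291. Power = Φ((0.09 − 1.960 × 0.0292)/0.0291) = 87.0%.

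Both agree with the stated 80% or better per test, at unadjusted 5%.

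**2. If any one result suffices.** With no true difference on any endpoint, independent tests give 1 − 0.95³ = 14.3% for a false result in either direction and 1 − 0.975³ = 7.3% for a false benefit. Simulation of correlated normal statistics (2 million draws per setting) gives:

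| Correlation | Any false difference | False benefit |
|---|---|---|
| 0 | 14.3% | 7.3% |
| 0.3 | 13.6% | 6.8% |
| 0.5 | 12.5% | 6.3% |
| 0.6 | 11.8% | 5.9% |

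If cognition is not counted as primary, two tests remain: 1 − 0.95² = 9.8% if independent, about 9.1% at correlation 0.5.

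**3. If all three must succeed.** The false-claim rate is at most 5%. Joint power at the planned effects is 0.795 × 0.795 × 0.870 = 55% if independent, 64% at correlation 0.5 and 66% at 0.6.

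**4. Power with family-wise control at 5%, 537 per arm.**
- First-step (Bonferroni) alpha 0.05/3 = 0.0167, critical value 2.394. PCS or MCS: Φ(2.786 − 2.394) = 65.2%, detectable difference (2.394 + 0.842) × √(2/537) = 0.197 SD. Cognition: Φ((0.09 − 2.394 × 0.0292)/0.0291) = 75.5%.
- Full Holm, all three planned effects true, correlation 0 to 0.6 (simulated): about 74-75% for PCS and for MCS, 81-83% for cognition.
- Fixed sequence, the two SF-36 scores and then cognition: 79.5% for the first test; second 0.795² = 63% if independent, rising to 69% at correlation 0.6; cognition 55-66%, the same as the joint power in step 3.

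**The case against.** The plan never says that one significant endpoint is enough. The primary specific aim in the synopsis joins quality of life and cognition with the word 'and', which can be read as requiring all of them. On that reading there is no inflation. This stands: a reader might infer that the trial simply runs at 12-14% error, but the documents do not support that without the condition. It does not rescue the plan, because requiring all three leaves joint power well short of 80%.

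The 12-14% also counts false results against the new tube, while the aim is to show benefit. That stands too; the false-benefit rate is about half as large, though still more than twice the 2.5% per test.

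A reader might suspect a hidden alpha split, because two-sided 0.025 with 0.40 vs 0.31 needs exactly 537 per arm. The text says five percent, however, and at 0.025 the power for 0.17 SD is only 70.7%, so no split was applied consistently.

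A reader might also infer that the synopsis ranks PCS, then MCS, then cognition. It supports quality of life before cognition, but it only names the two SF-36 scores together, and Section 10.2 discusses MCS first. Lastly, safety does not enter the 12-14%: Section 10.4.2 already gives it a separate one-sided 2.5% test.

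**Conclusion.** The point holds as an undefined success rule with no multiplicity control over three primary superiority tests. Under neither natural reading do the stated 5% and 80% both describe the primary aim:

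- Any one suffices: about 12-14% chance of a false difference, 6-7% of a false benefit.
- All three needed: at most 5% error, about 55-66% power.

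The error figures assume no true difference on any endpoint, the power figures assume every planned effect is true, and both assume common correlations of 0 to 0.6. The conflicting status of safety and of cognition is a separate inconsistency. A failed safety test might be thought to block a positive trial if safety is primary, but no section says so; that too depends on the missing success rule.

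**What to change.** Before unblinding, use the formal addendum that Section 10.2 provides for changes to the analysis plan to do the following.

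1. State what counts as meeting the primary aim, and control family-wise error at two-sided 5% across PCS, MCS and cognition. Holm is the sensible default because it needs no ordering.
2. Replace the power statement with the Holm figures in step 4 of the working. Give both the case where all planned effects hold and the more cautious first-step case, with its detectable difference of about 0.20 SD.
3. Use a fixed sequence only if the sponsor itself sets the order of PCS and MCS, and state the reduced power of the later tests. Anything after the first non-significant test becomes descriptive.
4. Give safety one status and cognition one status throughout the synopsis, Section 4 and Section 10. Keep safety's existing one-sided 2.5% test separate, and say whether non-inferiority is a condition for overall success.

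The cost is wording and lower stated power: under Holm, PCS and MCS fall from 79.5% to about 74-75% and cognition from 87% to about 81-83% if all planned effects hold. No new data are needed. Keeping 80% at the first-step alpha for 0.17 SD would take 725 per arm, so restating power is the practical course.
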